**RSV humoral immune responses**

Serological assays for the determination of functional antibodies against RSV-A and B will be performed by neutralization assays. Further characterization of the humoral immune response will be performed by use of enzyme-linked immunosorbent assays (ELISAs), including measurement of IgG antibodies binding to the RSVPreF3 protein and antibodies competing with monoclonal antibodies specific for binding to *RSB1 site* on RSVPreF3 (see [Table 10](#)). (*Amended, 13 May 2020*)

The assays will be performed at a GSK Biologicals' laboratory or in a laboratory designated by GSK Biologicals.

**Table 10      Humoral Immunity (Antibody determination) (*Amended, 13 May 2020*)**

System	Component	Method	Kit / Manufacturer	Unit	Cut-off s	Laboratory
Serum	Respiratory Syncytial Virus A Ab	NEUTRALIZATION	In-house	ED60	18	GSK Biologicals* or NÉOMED-LABS
Serum	Respiratory Syncytial Virus B Ab	NEUTRALIZATION	In-house	ED60	30	GSK Biologicals* or NÉOMED-LABS
Serum	RSVPreF3-specific IgG antibody concentrations	ELISA	In house at Neomed Labs	ELU/mL	25	Neomed Labs
Serum	RSVPreF3 RSB1 specific Ab	Competition ELISA	In-house	µg/mL	2.11	GSK Biologicals* or NÉOMED-LABS

Ab: antibody; ELISA: enzyme-linked immunosorbent assay; RSV: respiratory syncytial virus;

ED60: Estimated Dose: serum dilution giving a 60% reduction of the signal compared to a control without serum

\* GSK Biologicals laboratory refers to the Clinical Laboratory Sciences (CLS) in Rixensart, Belgium; Wavre, Belgium; Marburg, Germany.

**RSV cell-mediated immunity**

Evaluation of the CD4+ and CD8+ T-cell responses will be performed by use of an Intracellular Cytokine Staining (ICS) assay performed on peripheral blood mononuclear cells (PBMC) samples at GSK Biologicals' laboratory or in a laboratory designated by GSK Biologicals (see [Table 11](#)). Evaluation of B memory cells will be performed by ELISpot.

**CONFIDENTIAL**208851 (RSV OA=ADJ-002)  
Protocol Amendment 1 Final**Table 11 Cell-mediated Immunity (CMI)**

System	Component	Challenge	Method	Unit	Laboratory
PBMC	IL-2, CD40L, 4-1BB, TNF- $\alpha$ , IFN- $\gamma$ , IL-13, IL-17 secreting CD4+ and CD8+ T-cells	Peptide pool covering RSVPreF3	ICS	Events/10  cells	GSK Biologicals* or designated laboratory
PBMC	B-cell memory quantification	RSVPreF3	ELISPOT	Frequency of RSVPreF3-specific memory B-cells/10  B-cells	GSK Biologicals* or designated laboratory

PBMC: peripheral blood mononuclear cells; ICS: Intracellular cytokine staining

CD40L: cluster of differentiation 40 ligand; IFN- $\gamma$ : interferon gamma, IL (IL-2; IL-13; IL-17): interleukin;TNF- $\alpha$ : tumor necrosis factor alpha; 41BB (CD137)

\* GSK Biologicals laboratory refers to the CLS in Rixensart, Belgium; Wavre, Belgium; Marburg, Germany.

## Hematology and biochemistry

Hematology and biochemistry assays for safety assessment will be performed in a central laboratory (see [Table 12](#)).

**Table 12 Hematology/biochemistry**

System	Discipline	Component	Method	Scale**	Laboratory
Whole blood	Hematology	Leukocytes (White Blood Cells)	As per central laboratory procedure	Quantitative	Q  Solutions
		Neutrophils*			
		Lymphocytes*			
		Basophils*			
		Monocytes*			
		Eosinophils*			
		Hemoglobin			
		Platelets			
		Erythrocytes (Red Blood Cells)			
Serum	Biochemistry	Alanine Aminotransferase (ALT)			
		Aspartate Aminotransferase (AST)			
		Creatinine			
		Blood Urea Nitrogen (BUN)			
		Uric Acid			

\*For White Blood Cell (WBC) differential count.

\*\*Grading of laboratory parameters will be based on the Food and Drug Administration (FDA) Guidance for Industry

“Toxicity Grading Scale for Healthy Adult and Adolescent Volunteers Enrolled in Preventive Vaccine Clinical Trials” (refer to [APPENDIX C](#)). Basophils, monocytes, erythrocytes and uric acid are not included in the FDA Toxicity Grading Scale and will not be graded.

## RSV molecular biology

For identified RTI cases under active or passive surveillance, the potential RSV infection will be assessed by quantitative reverse transcription PCR (qRT-PCR) testing of nasal/throat swab specimen (see [Table 13](#)). Swab samples that are positive by RSV qRT-PCR will be tested by a multiplex PCR (panel of viruses) for detection of potential viral co-infection. Further assessment of samples negative by RSV qRT-PCR may be performed with multiplex PCR if deemed necessary.

**CONFIDENTIAL**208851 (RSV OA=ADJ-002)  
Protocol Amendment 1 Final**Table 13 Molecular Biology (PCR tests)**

Component	Kit / Manufacturer	Method	Unit	Laboratory
System: Nasal/throat swab specimen				
Respiratory Syncytial Virus A RNA Respiratory Syncytial Virus B RNA	In-house	Quantitative RT-PCR	Copies/ml	GSK Biologicals* or designated laboratory
Influenza A virus (Flu A) Influenza B virus (Flu B) Human respiratory syncytial virus A (RSV A) Human respiratory syncytial virus B (RSV B) Human Influenza A virus subtype H1 (Flu A-H1) Human Influenza A virus subtype H3 (Flu A-H3) Human Influenza A virus subtype H1pdm09 (Flu A-H1pdm09) Human adenovirus (AdV) Human metapneumovirus (hMPV) Human enterovirus (HEV) Human parainfluenza virus 1 (PIV1) Human parainfluenza virus 2 (PIV2) Human parainfluenza virus 3 (PIV3) Human parainfluenza virus 4 (PIV4) Human bocavirus 1/2/3/4 (HBoV) Human rhinovirus A/B/C (HRV) Human coronavirus 229E (229E) Human coronavirus NL63 (NL63) Human coronavirus OC43 (OC43)	Allplex Respiratory Panel or alternative	Multiplex PCR	Qualitative assay (positive/negative)	GSK Biologicals* or designated laboratory

Quantitative RT-PCR: quantitative reverse transcription polymerase chain reaction; RSV: respiratory syncytial virus

\* GSK Biologicals laboratory refers to the CLS in Rixensart, Belgium; Wavre, Belgium; Marburg, Germany.

### **Additional testing on blood or nasal/throat swab samples**

Additional testing on serum and frozen PBMC samples to characterise the immune response to RSV/to the investigational RSV vaccine/vaccine components may be performed if deemed necessary for accurate interpretation of the data and/or should such test(s) become available in the GSK Biologicals' laboratory or a laboratory designated by GSK Biologicals.

Additional viral/bacterial diagnosis testing on the nasal/throat swabs, such as (but not limited to) multiplex PCR, sequencing and/or high-throughput sequencing, may be done, if deemed necessary for accurate interpretation of the data and/or should such assays become available at GSK Biologicals' laboratory or a laboratory designated by GSK Biologicals.

Additional testing may include, but is not limited to, the following:

- Further characterisation of the pathogens detected in the nasal/throat swabs (e.g. genotyping, strain identification).
- Further characterization of the immune response directed against different epitopes of RSV F proteins.

**CONFIDENTIAL**208851 (RSV OA=ADJ-002)  
Protocol Amendment 1 Final

- Further characterization of the immune response by evaluation of cross-reactive neutralizing antibodies to human metapneumovirus (hMPV).
- Characterisation of the impact of vaccination on possible new immunological markers for protection (e.g. antibody affinity/avidity, ADCC).
- Host transcriptome signature: evaluation of mRNA and/or microRNA signatures by microarray and/or RNA sequencing.
- Translational research using next generation technologies.

Additional exploratory testing on the vaccine formulations and/or on the disease under study may be performed within the framework of the study if deemed necessary for accurate interpretation of the data or should such assay(s) become available at GSK Biologicals' laboratory or a laboratory designated by GSK Biologicals. These assays may not be represented in the objectives/endpoints of the study protocol and may be described in ancillary study protocol(s), as needed.

The GSK Biologicals' clinical laboratories have established a Quality System supported by procedures. The activities of GSK Biologicals' clinical laboratories are audited regularly for quality assessment by an internal (sponsor-dependent) but laboratory-independent Quality Department.

#### **5.9.4. Biological samples evaluation**

For blood sample collection, the following ranking applies:

1. Sample for hematology/biochemistry testing,
2. Sample for serological status to CMV testing (at Visit 1),
3. Sample for humoral immune responses,
4. Sample for CMI responses.

##### **5.9.4.1. Immunological read-outs (Amended, 13 May 2020)**

Testing of RSVPreF3 IgG antibodies will be performed on blood samples from all subjects, in both Part A and Part B, *except at Month 14 (Visit 8)*.

*Testing of RSV-A neutralizing antibodies will be performed on blood samples from all subjects, in both Part A and Part B, except at Month 8 (Visit 7) and Month 14 (Visit 8).*

Testing of RSV-B neutralizing antibodies will be performed on blood samples from all subjects in Part B.

Testing of RSVPreF3 **RSB1** specific antibodies will be performed on blood samples from a subset of subjects *at Day 31 or Day 91* in Part B who received the selected vaccine formulation and placebo (N $\geq$ 200).

**CONFIDENTIAL**208851 (RSV OA=ADJ-002)  
Protocol Amendment 1 Final

Testing of CD4+/CD8+ CMI will be performed on blood samples from all subjects in both Part A and Part B, *except at Month 8 (Visit 7) and Month 14 (Visit 8)*.

*At Month 8 (Visit 7) blood sample testing for humoral response pertaining to RSV-A neutralizing antibodies and CMI response will be performed for all subjects in Part B1; and for a subset of subjects in Part B2, who received a selected level of antigen dose and Placebo (N $\geq$ 460). Blood sample testing pertaining to the RSVPreF3 IgG antibodies will be performed for all subjects at Month 8 (Visit 7).*

*At Month 14 (Visit 8) humoral and CMI response testing will be performed for all subjects in Part B1; and for a subset of subjects in Part B2, who received a selected level of antigen dose and Placebo (N $\geq$ 460).*

Testing of memory B-cells will be performed on blood samples from a subset of subjects in Part B who received the selected level of antigen dose or placebo (N $\geq$ 400).

Testing of CMV IgG antibodies will be performed on blood samples from all subjects at Visit 1 (Day 1), in both Part A and Part B.

In case of insufficient blood sample volume to perform assays for all immunological read-out components, the samples will be analysed according to priority ranking provided in [Table 14](#) for Part A and [Table 15](#) for Part B.

**Table 14 Immunological read-outs in Part A**

Blood sampling time point		Sub-cohort	No. subjects	Component	Components priority rank
Type of contact and time point	Sampling time point				
Humoral immunity (on serum samples)					
visit 1 (Day 1)	Pre-Vacc	All subjects	~ 48	RSV-A neutralizing antibody	1
				Anti-RSVPreF3-specific IgG antibody	2
visit 3 (Day 31)	PI D31	All subjects	~ 48	RSV-A neutralizing antibody	1
				Anti-RSVPreF3-specific IgG antibody	2
visit 4 (Day 61)	PI D61	All subjects	~ 48	RSV-A neutralizing antibody	1
				Anti-RSVPreF3-specific IgG antibody	2
visit 6 (Day 91)	PII D91	All subjects	~ 48	RSV-A neutralizing antibody	1
				Anti-RSVPreF3-specific IgG antibody	2
Cell-mediated immunity (on PBMC samples)					
visit 1 (Day 1)	Pre-Vacc	All subjects	~ 48	CD4+/CD8+	-
visit 3 (Day 31)	PI D31	All subjects	~ 48	CD4+/CD8+	-
visit 4 (Day 61)	PI D61	All subjects	~ 48	CD4+/CD8+	-
visit 6 (Day 91)	PII D91	All subjects	~ 48	CD4+/CD8+	-

Pre-Vacc: Pre-vaccination; PI DX: Post-Dose 1 Study Day X; PII DX: Post-Dose 2 Study Day X; M: Month

PBMC: Peripheral Blood Mononuclear Cells

## CONFIDENTIAL

208851 (RSV OA=ADJ-002)  
Protocol Amendment 1 Final**Table 15 Immunological read-outs in Part B (Amended, 13 May 2020)**

Blood sampling time point*	Sub-cohort	No. subjects	Component	Components priority rank
Type of contact and time point				
Humoral immunity (on serum samples)				
visit 1 (Day 1)	Pre-Vacc	All subjects	~ 1000	RSV-A neutralizing antibody 1
				Anti-RSVPreF3-specific IgG antibody 2
		Subset	~ 200	RSV-B neutralizing antibody 3
visit 3 (Day 31)	PI D31	All subjects	~ 1000	RSVPreF3 RSB1 specific antibody 4
				RSV-A neutralizing antibody 1
				Anti-RSVPreF3-specific IgG antibody 2
visit 4 (Day 61)	PI D61	All subjects	~ 1000	RSV-A neutralizing antibody 1
				Anti-RSVPreF3-specific IgG antibody 2
				RSV-A neutralizing antibody 1
visit 6 (Day 91)	PII D91	All subjects	~ 1000	Anti-RSVPreF3-specific IgG antibody 2
				RSV-B neutralizing antibody 3
		Subset	~ 200	RSVPreF3 RSB1 specific antibody 4
visit 7 (Month 8)**	PII M8	Subset	~ 460	RSV-A neutralizing antibody 1
			~1000	Anti-RSVPreF3-specific IgG antibody 2
visit 8 (Month 14)***	PII M14	Subset	~ 460	RSV-A neutralizing antibody 1
				Anti-RSVPreF3-specific IgG antibody 2
Cell-mediated immunity (on PBMC samples)				
visit 1 (Day 1)	Pre-Vacc	All subjects	~ 1000	CD4+/CD8+ 1
		Subset	~ 400	Memory B-cells 2
visit 3 (Day 31)	PI D31	All subjects	~ 1000	CD4+/CD8+ 1
		Subset	~ 400	Memory B-cells 2
visit 4 (Day 61)	PI D61	All subjects	~ 1000	CD4+/CD8+ -
visit 6 (Day 91)	PII D91	All subjects	~ 1000	CD4+/CD8+ 1
		Subset	~ 400	Memory B-cells 2
visit 7 (Month 8)**	PII M8	Subset	~ 460	CD4+/CD8+ -
				Memory B-cells 2
visit 8 (Month 14)***	PII M14	Subset	~ 460	CD4+/CD8+ 1
		Subset	~ 400	Memory B-cells 2

Pre-Vacc: Pre-vaccination; PI DX: Post-Dose 1 Study Day X; PII DX: Post-Dose 2 Study Day X; M: Month

PBMC: Peripheral Blood Mononuclear Cells

\* Testing of additional time points for RSVPreF3 **RSB1** specific antibodies, RSV-B neutralizing antibodies and memory B-cells might be performed, should the results indicate that further investigation of the immune response is necessary.

\*\* At Visit 7, blood samples for RSV-A neutralizing antibody determination, and CMI determination will be tested from a subset of subjects (all subjects in part B1; and a subset of subjects in part B2, who received a selected level of antigen dose and Placebo).

\*\*\* At Visit 8, blood samples for antibody and CMI determination will be collected and tested from all subjects in part B1; and from a subset of subjects in part B2, who received a selected level of antigen dose and Placebo.

**CONFIDENTIAL**208851 (RSV OA=ADJ-002)  
Protocol Amendment 1 Final**5.9.4.2. Haematology/Blood Chemistry and CMV serology****Table 16 Hematology and biochemistry read-outs and CMV serology testing**

Blood sampling time point		Sub-cohort	No. subjects	Component
Type of contact and time point	Sampling time point			
Part A				
screening visit*	Pre-Day 1	All screened subjects	≥ 48	Hematology: leukocytes, neutrophils, lymphocytes, basophils, monocytes, eosinophils, hemoglobin, platelets, erythrocytes Biochemistry: ALT, AST, creatinine, BUN, uric acid
visit 1 (Day 1) visit 2 (Day 8) visit 4 (Day 61) visit 5 (Day 68)	Pre-Vacc PI D8 PI D61 PII D68	All enrolled subjects	~ 48	
visit 1 (Day 1)	Pre-Vacc	All enrolled subjects	~ 48	Anti-CMV IgG antibody
Part B				
screening visit*	Pre-Day 1	All screened subjects	≥ 48	Hematology: leukocytes, neutrophils, lymphocytes, basophils, monocytes, eosinophils, hemoglobin, platelets, erythrocytes Biochemistry: ALT, AST, creatinine, BUN, uric acid
visit 1 (Day 1) visit 2 (Day 8) visit 4 (Day 61) visit 5 (Day 68)	Pre-Vacc PI D8 PI D61 PII D68	All enrolled subjects	~ 1000	
visit 1 (Day 1)	Pre-Vacc	All enrolled subjects	~ 1000	Anti-CMV IgG antibody

Pre-Vacc: Pre-vaccination; PI DX: Post-Dose 1 Study Day X; PII DX: Post-Dose 2 Study Day X

ALT = Alanine Aminotransferase; AST = Aspartate Aminotransferase; BUN = Blood Urea Nitrogen

CMV = Cytomegalovirus

\* In case Visit 1 occurs more than 30 days after the Screening Visit, a re-screening visit should be scheduled before Visit 1 during which blood sample collection for safety laboratory assessment must be repeated (maximum one re-screening per subject is allowed). Only laboratory results from the re-screening visit, if it occurs, will be taken into consideration and recorded in the eCRF. Medical history, physical examination and review of inclusion/exclusion criteria must be repeated if a re-screening visit occurs. The subject can only be randomized once the investigator receives the results and confirms the eligibility criteria.

CONFIDENTIAL

208851 (RSV OA=ADJ-002)  
Protocol Amendment 1 Final**5.9.4.3. Molecular biology****Table 17 Molecular biology tests on nasal/throat swab specimen for Part B**

Sampling time point		Sub-cohort	No. subjects	Component
Type of contact (time point)	Sampling time point			
		Event-driven*	Event-driven*	RSV-A/B RNA
Sampling of nasal swab by subject at home Assessment visit for potential RSV-RTI	Unscheduled	All RSV-A/B positive swab samples**	All RSV-A/B positive swab samples**	Influenza A virus (Flu A) Influenza B virus (Flu B) Human respiratory syncytial virus A (RSV A) Human respiratory syncytial virus B (RSV B) Human Influenza A virus subtype H1 (Flu A-H1) Human Influenza A virus subtype H3 (Flu A-H3) Human Influenza A virus subtype H1pdm09 (Flu A-H1pdm09) Human adenovirus (AdV) Human metapneumovirus (hMPV) Human enterovirus (HEV) Human parainfluenza virus 1 (PIV1) Human parainfluenza virus 2 (PIV2) Human parainfluenza virus 3 (PIV3) Human parainfluenza virus 4 (PIV4) Human bocavirus 1/2/3/4 (HBoV) Human rhinovirus A/B/C (HRV) Human coronavirus 229E (229E) Human coronavirus NL63 (NL63) Human coronavirus OC43 (OC43)

\* RSV-A/B quantitative PCR (RSV-A/B RNA) will be performed on all specimen.

\*\* Respiratory Viruses Panel (Multiplex PCR) will be performed on all swabs RSV-A/B positive by qRT-PCR. Further assessment of RSV-A/B RNA negative samples may be performed with Multiplex PCR if deemed necessary.

**5.9.5. Immunological correlates of protection**

No generally accepted immunological correlate of protection has been demonstrated so far for the antigen used in the investigational RSV vaccine.

**5.10. Study procedures during special circumstances (Amended, 13 May 2020)**

*During special circumstances (e.g., COVID-19 pandemic), the specific guidance from local public health and other competent authorities regarding the protection of individuals' welfare and safety must be applied. For the duration of such special circumstances, the following measures may be implemented for enrolled participants:*

- *Instruction for the remaining scheduled visit (Visit 8): Planned study visit can proceed, if the study subjects are healthy and allowed to come to the site to have the blood sample and safety information collected. If the visit is impacted due to the national guidelines and/or site restrictions linked to the special circumstances, and it is not possible to collect the biological samples within the interval predefined in the protocol (see Table 8), the samples will be encoded as missing and encoded as protocol deviation. If the visit is impacted, the safety information (as per*

CONFIDENTIAL

208851 (RSV OA=ADJ-002)  
Protocol Amendment 1 Final

*protocol: SAEs, pIMDs, concomitant medications/vaccinations and intercurrent medical conditions) will be collected by site staff via telephone contact or other means of virtual contact, and this will not be considered as protocol deviation.*

- *Instruction for collection of home self-swabs in case study participant experiences suspected respiratory tract infection (RTI) symptoms: In case the investigator determines this is not posing additional risk to the subjects or household members, the subjects will be instructed to perform the home self-swab and keep it in their freezer (preferred) or refrigerator until recovered, and able to bring it to the site. If there is a possibility, a healthy relative can bring the sample to the site to be processed. In case investigator judges this is not advisable due to the national guidelines and/or site restrictions linked to the special circumstances, the self-swab will not be collected and the sample will be encoded as missing. Samples that are not collected will be documented as protocol deviations. The investigator and/or the site staff will provide these instructions to the subjects during the active surveillance contacts carried out every 2 weeks during the RSV season period.*
- *Instructions for assessment visit for suspected respiratory tract infection (RTI): Site staff will decide on the management of the cases (either having a site/different site location/home visit or by telephone contact) based on COVID-19 national guidelines and/or site restrictions linked to the special circumstances. If the nasal and throat samples cannot be collected at site, the sample will be encoded as missing. Samples that are not collected will be documented as protocol deviations. Biological samples will not be collected if they cannot be processed in a timely manner or appropriately stored until the intended use.*

*Impact on the per protocol set for immunogenicity will be determined on a case by case basis.*

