## **8.3. Assessment Visit for potential RSV-RTI**

The purpose of the Assessment Visit for potential RSV-RTI is to objectively document signs and symptoms (e.g., cough, runny nose, fever or difficulty to breath) by an appropriately qualified person (i.e., medical or nursing) and to take nasal and throat swabs for detection of RSV infection. The visit should take place as soon as possible after the start of symptoms (ideally within 48 hours, but no later than 7 days).

- Assessment visits may take place in the study participant's home, the investigator's clinical facility or a medical facility as appropriate to the circumstances in the judgment of the investigator.
- If the reported symptoms are already of a level of severity that urgent care is indicated, the study participant should be redirected to the proper location to receive this care (e.g. Emergency Room) and an assessment visit could be scheduled to take place there at a suitable time.
- For self-collection as well as staff-collection, swabs for analysis at sponsor laboratory should be collected when subjects show at least 3 of the following signs/symptoms:
  - Nasal congestion,
  - Sore throat,
  - Earache,
  - New or worsening cough,
  - New or worsening sputum,

**CONFIDENTIAL**208851 (RSV OA=ADJ-002)  
Protocol Amendment 1 Final

- Dyspnea,
- Rhinorrhea,
- Wheezing (whistling, musical or puffing sound made on exhalation) or worsening of wheezing,
- Rales (crackles),
- Rhonchi (sound with musical pitch during inspiration or expiration),
- Fever (temperature of  $\geq 37.5^{\circ}\text{C}$ ) or feeling feverish.
- During the assessment visit, the investigator/study staff will evaluate the clinical signs and symptoms of the RTI and measure the subject's resting vital signs (systolic/diastolic blood pressure, pulse oximetry, heart rate, respiratory rate after at least 10 minutes of rest) and temperature. RTI symptoms include, but may not be limited to, the following:
  - **Upper respiratory symptoms:** nasal congestion, sore throat, rhinorrhea, earache.
  - **Lower respiratory symptoms:** new or worsening cough, new or worsening of sputum production, dyspnea, wheezing or worsening of wheezing, rales (crackles), rhonchi.
  - **Systemic symptoms:** myalgia, arthralgia, fatigue, headache, decreased appetite, feverishness, pain (localized at chest or abdomen at respiration).
- Signs and symptoms and onset date of first symptom should be recorded within the RTI episode screen in the eCRF.

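### Section 5.10 permits home and off-site assessment visits for suspected RTI but codes the staff swab as missing unless it is collected at site, so a literal reading drops permitted swabs from the secondary RSV-RTI endpoint

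*Protocol*

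**What the plan says.** Section 5.10 lists the ways an assessment visit for a suspected RTI may be handled under special circumstances: "either having a site/different site location/home visit or by telephone contact". The next sentence sets the coding rule for the staff swab: "If the nasal and throat samples cannot be collected at site, the sample will be encoded as missing". Two further sentences complete the bullet: "Samples that are not collected will be documented as protocol deviations", and "Biological samples will not be collected if they cannot be processed in a timely manner or appropriately stored until the intended use".

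Section 8.3, which governs the visit in ordinary circumstances, is not tied to the site: "Assessment visits may take place in the study participant's home, the investigator's clinical facility or a medical facility", as the investigator judges appropriate.

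The swab feeds a named endpoint. Section 10.2 defines the Part B secondary endpoint of RSV-associated RTI by qRT-PCR on nasal/throat swabs collected during the assessment visit. Section 10.10 considers only episodes for which that visit took place with swab sampling. It analyses self-collected and staff-collected swabs separately and reports, by group on the Exposed Set, the proportion of subjects with at least one RSV-associated RTI. The self-collected swab supports only tertiary endpoints (Section 10.3).

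**The concern.** The bullet opens several places for the visit and then attaches the missing code to one of them. A site that follows the wording has two options after a home visit: not to swab, because a swab taken there would not count, or to swab and code the result missing. Either way the episode leaves the secondary endpoint, and the protocol provides no fallback to the self-swab for that endpoint.

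The amendment was written to add flexibility and, as far as possible, to promote data integrity. On this wording it is stricter than the standing rule in Section 8.3, at the time when home visits are most likely to be needed. Sites may also read it differently, so that the same home swab is tested at one centre and coded missing at another.

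**Working it through.** The protocol gives no expected RTI count, attack rate or missing-swab rate, so there is no stated figure to reproduce. The check compares the texts and then bounds how much follow-up the rule can touch.

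**Text comparison**

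| Handling of the episode | Allowed in 5.10? | Allowed in 8.3? | Staff swab under the literal 5.10 rule | Enters the secondary endpoint? |
|---|---|---|---|---|
| Visit at the site | yes | yes | valid | yes |
| Visit at a different site location | yes | yes, if a medical facility | unclear: depends on whether that location counts as the site | unclear |
| Home visit | yes | yes | missing | no |
| Telephone only | yes | not a visit | none taken | no |

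The home-visit row is the clear conflict. The telephone row is not affected: no staff swab exists there under either wording.

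**Upper bound on exposure**

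Inputs:
- The amendment is dated 13 May 2020, and Section 5.10 treats Visit 8 as the one scheduled visit remaining. I take this to mean that every subject had passed Visit 7 by then (assumption).
- Table 8: Visit 4 to Visit 7 is 170–190 days (optimal 180). Visit 4 to Visit 8 is 350–395 days (optimal 365).
- The RSV season runs approximately October to March (Section 3). I take 1 October 2020 as its start (assumption).

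Latest Visit 8 = 13 May 2020 + (Visit 4→8 interval − Visit 4→7 interval):
- Widest windows: 395 − 170 = 225 days, giving 24 December 2020, which is 84 days after 1 October, or 84 / 7 = 12 weeks.
- Optimal intervals: 365 − 180 = 185 days, giving 14 November 2020, which is 44 days.
- Narrowest windows: 350 − 190 = 160 days, giving 20 October 2020, which is 19 days.

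These figures are for the last subject. Anyone further ahead in follow-up has less, and a subject whose Visit 8 falls before October has none.

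**What a loss would do to the summary**

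Let p be a group's true RSV-RTI risk and m the share of its cases with no valid staff swab, with such cases not counted. Expected observed cases per 100 subjects = 100 × p × (1 − m). The values of p and m below are assumptions; neither is in the protocol.

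| p | m = 0 | m = 20% | m = 50% |
|---|---|---|---|
| 2% | 2.0 | 1.6 | 1.0 |
| 5% | 5.0 | 4.0 | 2.5 |
| 10% | 10.0 | 8.0 | 5.0 |

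Here m is a share of all the group's cases over the whole of Part B. Because the rule can act only in the short window above, m should lie well below the share of visits made at home within that window.

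If m is the same in every group, the ratio of two group proportions is unchanged, since p₁(1 − m) / [p₂(1 − m)] = p₁ / p₂. The absolute difference shrinks by the factor (1 − m).

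**The case against.** The best defence is that *at site* is loose wording for a swab taken by study staff. The rule concerns samples that could not be collected, and the following sentence logs uncollected samples as deviations, so the missing code may be meant only for a swab that does not exist. Section 8.3 allows home visits and Section 10.10 has no location limit. Nothing tells anyone to discard a swab already taken at home. This reading is plausible, but the text does not settle it. Section 10.10 also cannot recover a swab that a site did not take, or coded missing, because it followed Section 5.10.

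The points on impact stand. The RTI analysis is descriptive (Sections 10.10 and 10.11), the rule is the same for all groups, allocation is minimised on centre (Section 5.2.2.2.1), and formulation selection rests on safety and immunogenicity (Section 1.2.2).

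Two stronger readings are tempting, and the documents do not support them.

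- *Unswabbed episodes are recorded as RSV-negative.* Section 5.10 says missing, with a protocol deviation. Such a subject would look like a non-case if the denominator were every exposed subject, but that is an inference about the denominator and not something the protocol states.
- *Home-stored self-swabs will give false negatives.* Section 5.10 lets the subject "keep it in their freezer (preferred) or refrigerator until recovered, and able to bring it to the site" and gives no maximum number of days. But freezing is preferred, a relative may bring the swab in sooner ("If there is a possibility, a healthy relative can bring the sample to the site to be processed"), and the same section bars samples that cannot be appropriately stored. Section 5.8.1 refers self-swab details to the Study Procedures Manual (SPM), and Section 5.9 does so for storage of biological samples. The SPM is not at hand and may set a limit. The protocol gives no RNA-stability figure, so any loss of sensitivity would be invented, and the self-swab cannot alter the secondary endpoint.

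**Conclusion.** The inconsistency is real: the coding rule in Section 5.10 does not fit the visit locations allowed in the same bullet and in Section 8.3. Applied literally, it removes episodes seen at home, and possibly those seen at another location, from the secondary RSV-RTI endpoint.

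The severity is minor. Exposure is at most about 12 in-season weeks for the last subject and less for the others, given that all subjects had passed Visit 7 by 13 May 2020 and the season began about 1 October. The number of episodes affected cannot be derived from the protocol, and it is zero if every site reads the phrase loosely. The likely direction is a slightly low RSV-RTI proportion in all groups, with no reason in the text to expect a difference between them. The finding does not extend to false-negative results or to self-swab storage.

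**What to change.** In the assessment-visit bullet of Section 5.10, replace the condition that the sample cannot be collected at site with: *cannot be collected at the assessment visit, wherever it takes place (site, other location or home)*. Leave the existing sentence on timely processing and appropriate storage in force, so that a home swab that cannot be handled properly is still not taken.

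For self-swabs, at most add a cross-reference to the SPM for storage limits. Do not add a rule that recodes late negative self-swabs as missing while keeping late positives. Missingness would then depend on the result, and the proportion would be biased upwards if missing subjects are excluded.

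The cost is one phrase and a note to sites, with no additional visit, assay or form.
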